## 8.5.7. Adverse event causality assessment

For both serious and non-serious AEs, the investigator is required to assess the possible relationship between the AE and the study drug, i.e. to determine whether there exists a **reasonable possibility** that the study drug caused or contributed to the **AE(s)**.

The following categories for relationship to treatment will be used during AE reporting:

Related	There is at least a reasonable possibility of a causal relationship between an AE and an investigational medicinal product. This means that there are facts (evidence) or arguments to suggest a causal relationship
Not related	There is no reasonable possibility of causal relationship.

To help investigators with the decision binary tree (Related/Not related) in the evaluation of causality, the Council for International Organizations of Medical Sciences (CIOMS) VI group recommends that investigators be asked to consider the following before reaching a decision:

- Medical history (including presence of risk factors)
- Lack of efficacy/worsening of existing condition
- Study medications
- Other medications (concomitant or previous)
- Withdrawal of study medication, especially following trial discontinuation/EoS medication
- Erroneous treatment with study medication (or concomitant)
- Protocol related procedure.

# 8.5.8. Adverse event reporting requirements

Information on AEs must be evaluated by a physician. Each AE is to be classified by the investigator as serious or non-serious. This classification will determine the reporting procedure for the event.

All SAEs are to be notified immediately (within 24 hours of awareness of SAEs by the investigator) to the Sponsor at [contact]. This includes a description of the event, onset date and type, duration, severity, relationship to study drug, outcome, measures taken and all other relevant clinical and laboratory data.

NOTE: If the SAE form cannot be sent immediately, the sponsor can be immediately informed (within 24 hours of SAEs awareness by the investigator) by **telephone and/or SMS or by e-mail first**, and then additional relevant information will be shared within 2 to 3 additional calendar days, with or without the SAE report form.

The SAE form must be shared once it becomes available.

Any follow-up reports should be submitted within 2 working days of awareness in case of death or 5 working days of awareness for other cases.

SAE should also be reported on the clinical trial AE page of the eCRF. It should be noted that the form for reporting of SAE (SAE form) is not the same as the AE section of the eCRF. Where the same data are collected, the two forms must be completed in a consistent manner, and the same medical terminology should be used.

In addition, SAEs will be notified by the investigator or Sponsor to Ethics Committee/ Health Authorities as per local reporting requirements.

For more details about the process of SAE notification and reporting in the clinical trial AE page of the eCRF, please refer to the last version of the study procedure related to SAE notification (procedure DNDi-OXA-04-HAT SOP04) and to the last version of the eCRF completion guideline.

## 8.5.9. Exposure in utero

If any trial subject becomes or is found to be pregnant (based on start date of last menstruation period) while receiving an investigational drug or within 3 months after IP single dose administration, the investigator must notify the event (together with key information) to the Sponsor by email within 24 hours of awareness.

This must be done irrespective of whether an AE has occurred. The information submitted should include the anticipated date of delivery.

The investigator will follow the pregnancy until completion of the pregnancy or until pregnancy termination (i.e. induced/spontaneous abortion). The investigator will provide pregnancy follow-up or outcome information by email or once available on a "*Pregnancy Surveillance Form*" as a follow-up to the initial pregnancy notification.

Follow-up of the children exposed to drug in utero will be proposed to the pregnant participant by the Investigator, until the children reach 2 years of age and shall be reported using the "*Child Surveillance Form*".

As full data regarding both exposures during pregnancy and follow-up of new-born babies will be available after the trial reporting period, the associated analysis will be communicated as an addendum to previous submissions to regulators and policymakers.

A pregnancy is not a SAE. However, any unfavourable outcome meeting at least one seriousness criteria i.e. in the case of unfavourable pregnancy outcome (abortion, still birth) or congenital abnormality shall be notified to the sponsor as per same process as any SAE (within 24h of awareness by investigator, refer to 8.5.8). Once available, the "SAE form" must be shared (in addition to the **Pregnancy/Child Surveillance Form**).

# 8.5.10. Adverse event follow- up

All AEs should be followed until they are resolved; or the investigator assesses them as 'chronic' or 'stable'; or the subject's participation in the trial ends (i.e. until the EoS page in the CRF for the subject has been completed, or otherwise the last contact with the subject).

The following categories will be used to document each AE:

- Action taken: None, drug treatment, subject withdrawn, other (specified).
- Outcome: Completely recovered; recovered with sequelae; ongoing; not recovered; death; unknown.

In addition, all SAEs (related or not) and those non-serious AEs assessed by the investigator as possibly related to the investigational drug must continue to be followed even after the subject's participation in the trial is over. Such events should be followed until they resolve or until the investigator assesses them as "chronic" or "stable." Resolution of such events is to be documented on the AE page of the CRF and SAE form (if applicable).

## 9. Withdrawal criteria

## 9.1. Subject withdrawal from the study

A subject may withdraw from the trial at any time at their own request or may be withdrawn at any time at the discretion of the Investigator or Sponsor for safety, behavioural, or administrative reasons.

If a subject does not return for a scheduled visit, every effort should be made to contact the subject.

In any circumstance, every effort should be made to document subject outcome, if possible.

If the subject withdraws consent, no further evaluations should be performed and no attempts should be made to collect additional data, with the exception of safety data, which should be collected if possible and in accordance with subject consent.

If a subject withdraws from the study, and the reason is provided, this should be documented in the source note.

If a subject is withdrawn from the study because of a treatment limiting AE, thorough efforts should be made to clearly document the outcome of AE.

If a subject is withdrawn from the trial, the Investigator will make all necessary arrangements

to ensure that the subject receives the appropriate treatment for any relevant medical condition that may have caused the withdrawal.

Subjects withdrawn from the study will not be replaced.

# 9.2. Subjects lost to follow-up

If a subject misses the 4-month visit (-10 days to +1-month window) and can no longer be contacted by the study personnel, she/he will be considered as lost to follow-up. Before the subject can be considered as lost to follow-up, the study personnel must make every effort to re-establish contact with the subject or relatives as soon as possible to advise him/her of the importance of continuing in the study and to ascertain whether or not s/he wishes to and/or should continue in the study. These contact attempts should be documented in the participant's medical record.

A subject declared as lost to follow-up was replaced in order to maintain the planned sample size. From 5 months after the start of the study, the rate of subjects lost to follow-up was regularly assessed to ensure 1200 subjects will complete the 4 months of follow-up. However, given the low rate of lost to follow-up subjects after 1.5 year of study conduct, it was agreed that not replacing the subjects lost to follow-up will not impact the statistical power of analysing the primary objective since the subjects will be included in the safety analysis set.

# 10. Data analysis and statistical methods

Full details of the statistical methods are provided in the statistical analysis plan.

# 10.1. Sample size and ratio determination

## 10.1.1. Sample size determination

The sample size was determined based on statistical probabilities to detect uncommon TEAEs in the active treatment (acoziborole) group (see Table 5). The definition for an uncommon event is a relative frequency between 0.1% and 1%. The median relative frequency is therefore 5/1000 (0.5%). The probability to detect at least 1 event if the true incidence rate is 0.5% is as high as 98% with 900 subjects and the probability is 83.5% for a true incidence rate of 2/1000 (0.2%). According to the calculations, 900 subjects exposed to acoziborole shows a high probability (>99%) of detecting at least one event (if the incidence rate is 1%) with a similar probability when exposing 1200 subjects. Therefore, 900 subjects will be administered with acoziborole and 300 subjects with placebo, for an overall sample size of 1200 subjects.

Table 5. Statistical probabilities for detecting uncommon treatment-emergent adverse
events (TEAEs) in the acoziborole group

Objectives/sample size (safety)	N=900	N=1200
Chance of detecting at least one event if the incidence rate is 1%	99.9%	99.99%
Chance of detecting at least one event if the incidence rate is 0.1%	59.36%	68.89%
Precision: 95% exact CI if one event is observed	0.003-0.6%	0.002-0.46%
Precision: 95% exact CI if three events are observed	0.068-0.97%	0.052-0.73%

CI=confidence interval; TEAEs=treatment-emergent adverse events.

Uncommon TEAEs are those with frequency  $\geq 1/1000$  and < 1/100 as per regulatory guidelines.

# Sample size calculation for the TrypSkin exploratory sub-study:

The primary objective is to estimate the prevalence of dermal extravascular T.b. gambiense trypanosomes in a population of seropositive subjects non-confirmed parasitologically. Preliminary results from Guinea, on a limited number of subjects, have shown that all seropositive individuals presenting a positive CATT test in plasma dilution ≥1:4, but nonconfirmed by parasitological examination of blood and lymph, had parasites in skin biopsies (15). Knowing that approximately 25% of the RDT positive subjects non-confirmed parasitologically present a positive CATT test in plasma dilution ≥1:4, it is hypothesized that up to 20-25% of the population of RDT positive subjects non-confirmed parasitologically enrolled in the TrypSkin exploratory sub-study could possibly carry dermal extravascular parasites. Bearing in mind this higher limit of the skin-dwelling trypanosome prevalence, we have estimated the minimum sample size required to be able to evaluate the real prevalence with a satisfactory precision (a narrow confidence interval [CI]). Under the assumption that skin-dwelling trypanosomes could be observed in up to 20-25% of the 1200 subjects, to obtain a 95% CI with a precision of 3%, a minimum of 690 evaluable subjects is required (Table 6). Based on these calculations and taking into account a provision of 5% (35 subjects) to allow for skin samples that are non-analysable, the target number of subjects to be enrolled in the TrypSkin exploratory sub-study is 725.

	Estimated prevalence					
Precision	0.05	0.10	0.15	0.20	0.25	0.30
0.025	300	550	780	980	1160	1300
0.03ª	200	390	540	690	800	900
0.05	80	130	200	245	290	320

CI=confidence interval.

a. Width of 95% CI approximately 0.06 (6%)

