Sample size	regimen on Day 1 of the study The sample size was determined based on statistical probabilities to detect uncommon TEAEs in the active treatment (acoziborole) group. The definition for uncommon event is a relative frequency between 0.1% and 1%. The median relative frequency is therefore 5/1000 (0.5%). The probability to detect at least 1 event if the true incidence rate is 0.5% is as high as 98% with 900 subjects and the probability is 83.5% for a true incidence rate of 2/1000 (0.2%). According to the calculations, 900 subjects exposed to acoziborole shows a high probability (>99%) of detecting at least one event (if the incidence rate is 1%) with a similar probability when exposing 1200 subjects. Therefore, 900 subjects will be administered with acoziborole and 300 subjects with placebo, for an overall sample size of 1200 subjects. Sample size calculation for the TrypSkin exploratory sub- study:					
	The primary objective is to estimate the prevalence of dermal extravascular T.b. gambiense trypanosomes in a population of seropositive subjects non-confirmed parasitologically. Preliminary results from Guinea, on a limited number of subjects, have shown that all seropositive individuals presenting a positive CATT test in plasma dilution ≥1:4, but non-confirmed by parasitological examination of blood and lymph, had parasites in skin biopsies. Knowing that approximately 25% of the RDT positive subjects non-confirmed parasitologically present a positive CATT test in plasma dilution ≥1:4, it is hypothesised that up to 20-25% of the population of RDT positive subjects, non-confirmed					

	parasitologically, enrolled in the TrypSkin exploratory sub-study could possibly carry dermal extravascular parasites. Bearing in mind this higher limit of the skin-dwelling trypanosome prevalence, we have estimated the minimum sample size required to be able to evaluate the real prevalence with a satisfactory precision (a narrow confidence interval [CI]). Under the assumption that skin-dwelling trypanosomes could be observed in up to 20-25% of the 1200 subjects, to obtain a 95% CI with a precision of 3%, a minimum of 690 evaluable subjects is required. Based on these calculations and taking into account a provision of 5% (35 subjects) to allow for skin samples that are non-analysable, the target number of subjects to be enrolled in the TrypSkin exploratory sub-study is 725.

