## 10.1.2. Ratio determination

Operational properties of various allocation ratios for the following assumptions are as follows:

- 1. Total sample size (for safety main study): n=1200 (900 acoziborole and 300 placebo)
- 2. Excess rate (ER) for safety: 1% (acoziborole = 2% of AEs of interest, Placebo = 1%)
- 3. Probability to detect an infrequent AE ( $\leq 1\%$  upper limit of class)
- 4. Probability to detect an infrequent AE (0.5% mid-class)

5. Total sample size for efficacy (TrypSkin exploratory sub-study): n=725 in order to ensure a minimum of 700 evaluable biopsies

6. Binary endpoint for efficacy: success=no tryps detected in punch skin at month 4, failure = at least one tryp-positive result in punch skin at Month 4

7. Probability to detect at least one trypanosome in derma at baseline: 20%

8. No effect of placebo on occurrence of tryps in derma at month 4: failure rate at 4 months=20%

9. Effect of 95% of acoziborole on occurrence of tryps in derma at Month 4 (efficacy): failure rate at Month 4 =  $0.05 \times 0.20 = 0.01$  or 1%

10. Excess rate of success in acoziborole group: 19% (assuming the same efficacy as stage 2 patients)

	Safety			Efficacy (for TrypSkin sub-study)		
Allocation ratio	Sample size for safety	Exact 95% CI limits of ER	Probability to detect an infrequent AE if occurrence rate = 1% (upper limit), = 0.5% (mid-class) and = 0.1% (lower limit of class)	Sample size for efficacy	Exact 95% CI limits of ER Estimate = 20%	Power (chance to detect a difference vs PBO) if acoziborole efficacy is 95%
3:1	PBO = 300 ACO = 900	Lower = -0.92% Upper = +2.41%	Upper: 99.99% Mid: 99.90% Lower: 59.36%	PBO = 175 ACO = 525	Lower = 13.38% Upper = 25.55%	99.99%
2:1	PBO = 400 ACO = 800	Lower = -0.64 Upper = +2.42%	Upper: 99.96% Mid: 98.18% Lower: 55.06%	PBO = 233 ACO = 467	Lower =14.02% Upper = 24.62%	99.99%
3:2	PBO = 480 ACO = 720	Lower = -2.30%* Upper = +0.66%*	Upper: 99.93% Mid: 97.29% Lower: 51.34%	PBO = 280 ACO = 420	Lower = 14.51% Upper = 24.15%	99.99%
1:1	PBO = 600 ACO = 600	Lower = -0.44% Upper = +2.51%	Upper: 99.75% Mid: 95.06% Lower: 45.23%	PBO = 350 ACO = 350	Lower: 14.81% Upper: 23.48%	99.99%

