2.4.2. Sample size for the TrypSkin study

For TrypSkin sub-study, the primary objective is to estimate the prevalence of extravascular dermal *T.b. gambiense* trypanosomes in a population of seropositive subjects non-confirmed parasitologically. Preliminary results from Guinea, on a limited number of subjects, have shown that all seropositive individuals presenting a positive CATT test in plasma dilution \geq 1:4, but non-confirmed by parasitological examination of blood and lymph, had parasites in skin biopsies⁸. Knowing that approximately 25% of the RDT positive subjects non-confirmed parasitologically present a positive CATT test in plasma dilution \geq 1:4, it is hypothesized that up to 20-25% of the population of RDT-positive subjects non-confirmed parasitologically enrolled in the TrypSkin

study could possibly carry dermal extravascular parasites. Bearing in mind this higher limit of the skin-dwelling trypanosome prevalence, we have estimated the minimum sample size required to be able to evaluate the real prevalence with a satisfactory precision (a narrow CI). Under the assumption that skin-dwelling trypanosomes could be observed in up to 20-25% of the 1,200 subjects, to obtain a 95% confidence interval with a precision of 3%, a minimum of 690 evaluable subjects is required. A provision of 5% (35 subjects) is planned in case skin samplings would be non-analyzable. Overall, the number of subjects to be enrolled in the TrypSkin ancillary study is therefore 725. The determined sample size is guided by the expected precision as presented in Table 2.4.2.1.

	Estimated Prevalence								
	0.05	0.10	0.15	0.20	0.25	0.30			
0.025	300	550	780	980	1160	1300			
0.03 ^{Error!} Reference source not found.	200	390	540	690	800	900			
0.05	80	130	200	245	290	320			

Table 2.4.2.1: Sample sizes and corresponding precision for TrypSkin exploratory study

CI=confidence interval

^a Width of 95% CI approximately 0.06 (6%)

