2.4.3. Ratio determination

Operational properties of various allocation ratios for the following assumptions are as follows:

- 1. Total sample size (for safety main study): n=1200, (900 acoziborole and 300 placebo)
- 2. Excess rate of 1% (acoziborole = 2% of AEs of interest, Placebo = 1%) for safety purposes
- 3. Probability to detect an infrequent AE ($\leq 1\%$ upper limit of class)
- 4. Probability to detect an infrequent AE (0.5% mid-class)
- 5. Total sample size (TrypSkin exploratory sub-study): n=700
- 6. Binary endpoint: Success = no tryps detected in punch skin at month 4 (failure = at least one tryp-positive result in punch skin at Month 4)
- 7. Probability to detect at least one trypanosome in derma at baseline: 20%
- 8. No effect of placebo on occurrence of tryps in derma at month 4: failure rate at 4 months = 20%
- 9. Effect of 95% of acoziborole on occurrence of tryps in derma at Month 4 (efficacy): Failure rate at Month 4 = $0.05 \times 0.20 = 0.01$ or 1%.
- **10.** Excess rate of success in acoziborole group = 19% assuming the same efficacy as stage 2 patients.

Table 2.4.3.1 presents the summary of the results for different assumptions on precision and power for the study to determine the required ratio.

	Safety			TrypSkin sub-s	TrypSkin sub-study				
Allocation ratio	Sample size for main study	Exact 95% Confidence interval limits of excess rate	Probability to detect an unfrequent AE if occurrence rate = 1% (upper limit), = 0.5% (mid-class) and = 0.1% (lower limit of class)	Sample size for sub-study	Exact 95% CI limits of excess rate Estimate = 19%	Power (chance to detect a difference vs pbo) if acoziborole efficacy is 95%			
3:1	PBO = 300 ACO = 900	Lower = -0.92% Upper = +2.41%	Upper: 99.99% Mid: 99.90% Lower: 59.36%	PBO = 175 ACO = 525	Lower = 13.38% Upper = 25.55%	99.99%			
2:1	PBO = 400 ACO = 800	Lower = -0.64 Upper = +2.42%	Upper: 99.96% Mid: 98.18% Lower: 55.06%	PBO = 233 ACO = 467	Lower =14.02% Upper = 24.62%	99.99%			
3:2	PBO = 480 ACO = 720	Lower = -2.30%* Upper = +0.66%*	Upper: 99.93% Mid: 97.29% Lower: 51.34%	PBO = 280 ACO = 420	Lower = 14.51% Upper = 24.15%	99.99%			
1:1	PBO = 600 ACO = 600	Lower = -0.44% Upper = +2.51%	Upper: 99.75% Mid: 95.06% Lower: 45.23%	PBO = 350 ACO = 350	Lower: 14.81% Upper: 23.48%	99.99%			

*Not comparable with other allocation ratio due to decimal digits in the number of subjects requiring rounding to the closest entire number

Conclusions:

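### TrypSkin's 690 evaluable subjects give ±3% precision only up to about 20% prevalence; at the 25% upper limit named in the text, the plan's own table requires 800

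*Protocol*

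**What the plan says.** Protocol 10.1.1 (TrypSkin part) reasons that about a quarter of RDT-positive unconfirmed subjects have a CATT titre of 1:4 or above. In preliminary Guinean data, all such subjects had skin parasites, so prevalence is hypothesised to reach 20–25%. It continues: "Bearing in mind this higher limit of the skin-dwelling trypanosome prevalence, we have estimated the minimum sample size required", and concludes that "to obtain a 95% CI with a precision of 3%, a minimum of 690 evaluable subjects is required", citing Table 6. The Protocol summary carries the same argument. SAP 2.4.2 repeats it: "to obtain a 95% confidence interval with a precision of 3%, a minimum of 690 evaluable subjects is required".

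Enrolment is then raised to 725, using "a provision of 5% (35 subjects) to allow for skin samples that are non-analysable".

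Two related statements appear in the allocation-ratio sections:

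- **Evaluable number.** Protocol 10.1.2 item 5 has "n=725 in order to ensure a minimum of 700 evaluable biopsies", and SAP 2.4.3 item 5 has "Total sample size (TrypSkin exploratory sub-study): n=700".
- **Detection probability, main safety study.** The 3:1 row of Protocol Table 7 and SAP Table 2.4.3.1 reads "Upper: 99.99% Mid: 99.90% Lower: 59.36" (per cent). The Protocol summary, Protocol 10.1.1 and SAP 2.4.1 instead say: "The probability to detect at least 1 event if the true incidence rate is 0.5% is as high as 98% with 900 subjects".

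**The concern.** The text names a prevalence range, says the size allows for its upper end, and gives 690 as the minimum. The table it cites puts 690 under 20% and 800 under 25%, so the number answers the lower end of the range only.

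Estimating prevalence is the stated primary objective of the sub-study, and ±3% is the criterion from which 690, and hence 725, is derived. A reader who relies on the text would expect ±3% to hold at 25%, and it does not.

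The two side points are internal contradictions. One enrolment figure is said to yield two different evaluable numbers, and one detection probability is printed with two different values.

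**Working it through.** **Inputs.** Two-sided 95% confidence, z = 1.96. Precision d = 0.03 is a half-width, because the Table 6 footnote gives a full width of about 6%. Planning prevalence is 20% to 25%; evaluable 690; provision 35; enrolled 725 (all Protocol 10.1.1).

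**Reproducing Table 6.** n = z² p(1−p)/d²:

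- p = 0.20: 3.8416 × 0.16 / 0.0009 = 682.9 (table: 690)
- p = 0.25: 3.8416 × 0.1875 / 0.0009 = 800.3 (table: 800)

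The other cells of the 0.03 row also reproduce to rounding, so the table rests on this normal approximation.

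**Precision that 690 delivers.** Half-width = 1.96 √(p(1−p)/690):

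| Prevalence | Half-width, 690 evaluable |
|---|---|
| 10% | 2.24% |
| 15% | 2.66% |
| 20% | 2.98% |
| 25% | 3.23% |

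Setting the half-width to 0.03 gives p(1−p) = 690 × 0.0009 / 3.8416 = 0.1616, so p = 20.3%. If all 725 enrolled subjects were analysable, the half-width at 25% would still be 3.15%.

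**Other interval methods.** The number needed at 25% is 798 with Wilson and 832 with Clopper–Pearson. With 690 evaluable, the half-widths at 25% are 3.22% and 3.30%. No method tried gives ±3% at 25% with 690. A finite-population correction with N = 1200 does not explain 690 either: it would give about 435 at 20% and 480 at 25%.

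**Enrolment.** 690 × 1.05 = 724.5, rounded to 725. The same provision applied to 800 gives 800 × 1.05 = 840.

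**Side point (a), 690 or 700 evaluable.** 725 − 35 = 690, whereas 700 evaluable would allow a loss of only 25. Table 7 uses 175 + 525 = 700. A Wald 95% interval for the assumed 20% − 1% = 19% difference is:

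- 175 + 525: 0.19 ± 1.96 √(0.20×0.80/175 + 0.01×0.99/525) = 13.01% to 24.99%
- 172.5 + 517.5 (total 690): 12.97% to 25.03%

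Each limit moves by less than 0.05 points. The table prints exact limits (13.38% to 25.55%), so this comparison shows only the size of the shift.

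**Side point (b), detection probability.** P(at least one event) = 1 − (1 − 0.005)^n:

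| Exposed | Recomputed | Printed |
|---|---|---|
| 900 | 98.90% | 99.90% |
| 800 | 98.19% | 98.18% |
| 720 | 97.29% | 97.29% |
| 600 | 95.06% | 95.06% |

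Only the 3:1 cell fails to reproduce, which looks like a one-digit slip. The chance of missing such an event is 1.10%, not 0.10%.

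**The case against.** The strongest case is that this is loose wording with almost no consequence. Table 6 is cited in the same sentence and shows both 690 and 800. The prevalence is put forward only as a possibility, and the allocation-ratio sections plan on 20% alone, the column 690 comes from. At any prevalence below about 20% precision is better than promised. The sub-study is exploratory, and the prevalence thresholds that trigger action are at 2%. The reported interval will come from the data. Table 7 also gives the size some separate support, through about 99.99% power for the efficacy comparison. All of this stands, and it is why no change in enrolment is proposed. It does not make the sentence correct: the text says the size reflects the higher limit, and its own rationale points to 25%.

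A fair technical reservation is that ±3.0% and ±3.2% hold for Wald and Wilson intervals, whereas exact intervals with 690 give 3.05% and 3.30%. No interval method was found specified for the TrypSkin prevalence, so the corrected sentence should name its method.

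On the side points, planning for 700 does satisfy a minimum of 690, and nothing in the documents says which number must prevail; what needs removing is the contradiction. The 98% in the text is a truncation of 98.9% rather than an error, so changing it is optional.

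**Conclusion.** The concern holds. The stated ±3% is met up to a prevalence of about 20.3% and missed at the 25% limit, where 690 evaluable subjects give about ±3.2% and the plan's own table asks for 800 (840 enrolled with its 5% provision, against 725). This rests on the normal approximation that reproduces Table 6 and on reading precision as a half-width, as the table footnote states.

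The effect is small: about 0.2 points of half-width, no effect on any decision rule, and no case for enrolling more. The side points are also confirmed, and they change neither the 3:1 allocation nor the 900 exposed. At 98.90%, detection at 0.5% incidence still exceeds the 95% target in Protocol 3.3, and 3:1 still has the highest mid-class value.

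**What to change.** Keep enrolment at 725. In the Protocol summary, Protocol 10.1.1 and SAP 2.4.2, replace the precision statement with: *690 evaluable subjects give approximately ±3.0% at 20% prevalence and ±3.2% at 25% (normal approximation).*

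Separately:

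- **(a)** Reconcile the evaluable number in Protocol 10.1.2 item 5 and SAP 2.4.3 item 5 with 690. Label the TrypSkin columns of Protocol Table 7 and SAP Table 2.4.3.1 as based on 700; recomputing them is optional given the size of the shift.
- **(b)** Correct the 3:1 mid-class cell in both tables to 98.90%. Optionally, change 98% to 98.9% in the Protocol summary, Protocol 10.1.1 and SAP 2.4.1 so that text and table agree.

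The cost is text and table edits, with no added participants and no change to any analysis. The stated precision at 25% becomes slightly less favourable. Protocol edits follow the amendment procedure in Protocol 13, so they are best made together with other changes.
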